4.5.2 Discontinuation From the Study

Participation of a patient in this study may be discontinued for any of the following reasons:

- Patient requests discontinuation or withdraws consent to participate in the study for any reason;
- Discovery of an unexpected, serious, or unacceptable risk to the patients enrolled in the study;
- Demonstration of efficacy that would warrant study stopping;
- Study data are not sufficiently complete and/or evaluable;
- Determination of futility;
- The Sponsor decides to suspend or discontinue testing, evaluation, or development of the study treatment; and/or
- The regulatory authority decides to terminate the study.

4.5.3 Discontinuation of Enrollment Criteria

Discontinuation of enrollment will occur for Phase 2a patients who meet any of the following criteria:

[figure not shown]
- Any CTCAE Grade 5 toxicity attributed to CyPep-1;
- SUSAR ≥Grade 4 CTCAE attributed to any component of the treatment combination;
- Signal of increased frequency or severity of any irAEs leading to permanent discontinuation as defined in Table 10;
- Site of injection AEs ≥Grade 4 CTCAE caused by CyPep-1 that do not revert to ≤Grade 1 in a 2 week period; or
- Any CyPep-1 related toxicity resulting in liver abnormality meeting Hy's Law criteria.

[figure not shown]
The observation of any of these criteria must trigger the immediate decision by the Sponsor to stop recruitment and organize an urgent DMC meeting, which will assess the causality of the observed AEs and the fulfillment of the discontinuation of enrollment criteria (above). The DMC will formulate a recommendation to resume recruitment, discontinue the involved cohort, or stop the study.

If a patient withdraws prematurely from the study due to the above criteria or any other reason, study staff should make every effort to complete the full panel of assessments scheduled for the EoT Visit (7 [±2] days after the last CyPep-1 or pembrolizumab administration). Withdrawal from the study will not affect or prejudice the patient's further care or treatment.

In the case of a patient lost to follow-up, attempts to contact the patient must be made and documented in the patient's medical records.

Patients who are discontinued from the study before receiving at least 1 dose of study treatment will be replaced. Patients who are discontinued from the study after receiving at least 1 dose of CyPep-1 or pembrolizumab will not be replaced. In case of pembrolizumab-related toxicity (≥Grade 2 according to the NCI CTCAE v5.0), treatment with CyPep-1 will be delayed and planned after a review by the Investigator and Medical Monitor. If CyPep-1 treatment is delayed >7 days, that dose will be omitted. After 14 days of delay, consult with the Sponsor. See Section 5.5.3.3 for management of dose toxicity.

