CyPep-1 will be administered Q2W as an IT injection. CyPep-1 will be administered through a needle, which should be redirected along multiple tracks to ensure even dispersion of CyPep-1 throughout the tumor lesion. On the visits that CyPep-1 and pembrolizumab are administered on the same day, CyPep-1 is to be administered 30 to 60 minutes **after** pembrolizumab infusion is completed. Following CyPep-1 administration, patients must be observed for 4 hours post injection at Cycle 1 Visit 1 and Cycle 2 Visit 1 and 1 hour post injection at Cycle 1 Visit 2 and

Cycle 1 Visit 3 for potential immediate injection-related reactions. Refer to the Guidance for Intra-tumoral Administration of CyPep-1 study manual for more details.

The cumulative maximal injected volume of CyPep-1 will be 4 mL (cumulative maximal dose of 20 mg at the recommended 5 mg/mL concentration) per treatment day for each patient, and it may be divided for injection over 1 to 3 tumor lesions (satellitosis/grouped lesions <1 cm count as 1 lesion) depending on tumor lesion size; see Table S3. The injected lesions identified at baseline should be injected 3 times before selecting new lesions to inject, unless there is a complete response or the lesion, by the Investigator's assessment, has been adequately treated (eg, reduced size and highly inflamed). The volume of CyPep-1 delivered to each injected lesion will be determined based on the longest diameter of the lesion. Effort should be made to administer the maximum volume of CyPep-1 as planned per lesion size; see Table S3.

Pembrolizumab Administration

The dose of pembrolizumab in combination with CyPep-1 will be 400 mg Q6W administered via a 30-minute infusion, beginning at Cycle 1 Visit 1. On the visits that CyPep-1 and pembrolizumab are administered on the same day, CyPep-1 is to be administered 30 to 60 minutes **after** pembrolizumab infusion is completed. Pembrolizumab may be administered up to 3 days before or after the scheduled Visit 1 of each cycle from Cycle 2 onward.

The Pharmacy Manual contains specific instructions for the preparation of the pembrolizumab infusion and administration of infusion solution.

SAFETY VARIABLES:

Safety will be assessed by physical examinations, vital signs, 12-lead electrocardiograms (ECGs), ECOG performance status, laboratory evaluations, and AEs (as defined by NCI CTCAE v5.0) as indicated in the Schedule of Assessments. Additional assessments may be performed as clinically indicated.

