AEs will be recorded from the time of signing the ICF until 30 days after the last dose of study treatment. All AEs that are considered serious will be monitored and recorded until 90 days (30 days if patients initiate new anti-cancer therapy) after the last dose of study treatment. Other safety assessments will be conducted as described in the Schedule of Assessments (Appendix A). The Data Monitoring Committee (DMC) will review accumulating safety data in regular intervals as per the DMC charter.

An overview of the study flow is presented in Figure 3.

Figure 3. Study Flow

The Phase 1b portion of the study will comprise of the first 6 patients enrolled in the study. After the first 6 patients have completed the DLT period (Cycle 1 [initial 6 weeks of study treatment]), the DMC and Sponsor will review safety and tolerability data prior to the enrollment of the remainder of the patients into the Phase 2a portion of the study.

DLT = dose-limiting toxicity; DMC = Data Monitoring Committee; EoT = End of Treatment; FU = follow-up; IT = intra-tumoral(ly); IV = intravenous(ly); n = number of treatment cycle; Q6W = every 6 weeks; Q8W = every 8 weeks; Screen = screening.

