3.1.1 Phase 1b

The Phase 1b portion of the study will comprise of the first 6 patients enrolled in the study to confirm the recommended CyPep-1 dose (20 mg Q2W) based on safety and tolerability observations.

Patients will receive IT injections of a fixed concentration of CyPep-1 Q2W beginning at Cycle 1 Visit 1. Pembrolizumab will be administered IV at a fixed dose Q6W beginning at Cycle 1 Visit 1. Patients must be observed for 4 hours post injection for PK monitoring on Cycle 1 Day 15. The plasma concentration-time profile of CyPep-1 and, if detectable, the derived PK parameters will be assessed.

The DLT period for the Phase 1b portion of the study will be Cycle 1 (initial 6 weeks of study treatment); see Section 3.1.1.1. After the first 6 patients have completed the DLT period, the DMC and Sponsor will review safety and tolerability data prior to the enrollment of the patients into the Phase 2a portion of the study. If \leq 2 DLTs are observed in the first 6 patients, then the recommended CyPep-1 dose will be confirmed and enrollment of the remainder of the patients should continue.

If >2 of the 6 patients develop a DLT at the recommended CyPep-1 dose level (5 mg/mL dose concentration), then the MTD of CyPep-1 will be assumed to have been exceeded and dose de-escalation will be conducted to determine the MTD. At least 6 patients will be treated at CyPep-1 dose level -1 (2 mg/mL dose concentration). If necessary, due to >2 DLTs in the dose level -1 cohort, a further reduction to dose level -2 (0.5 mg/mL dose concentration) will be performed.

Dose de-escalation will proceed according to the following rules:

- If 2 out of 6 patients develop a DLT, the MTD will be declared; or
- If >2 out of 6 patients develop a DLT, the dose will be de-escalated to the next lower dose.

The MTD will guide confirmation, by agreement of the DMC and the Sponsor, of a recommended Phase 2 dose (RP2D). The RP2D may be equivalent to the MTD or may be a dose below the MTD and will be dependent on an acceptable tolerability profile and manageable AEs.

The patients from Phase 1b will continue to the Phase 2a portion of the study. After the DMC reviews the safety data, feedback will be provided to the Sponsor regarding the further conduct of the study, see Section 3.1.2.

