- 8. Any single instance of aspartate aminotransferase and/or alanine aminotransferase >3 × upper limit of normal (ULN) AND concurrent total bilirubin >2 × ULN that is not thought to be due to disease progression or other medical illness (ie, liver function abnormalities that meet the criteria of Hy's Law);
- 9. Any treatment-related toxicity that causes the patient to discontinue treatment during Cycle 1;
- 10. Missing >25% of study treatment doses as a result of drug-related AE(s) during the first cycle;
- 11. Grade 5 toxicity.

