2.3 Study Design

2.3.1 Overview

This is an open-label, multi-center, non-randomized Phase 1b/2a study. The Phase 1b portion of the study (the first 6 patients enrolled) will confirm the recommended CyPep-1 dose of 20 mg every 2 weeks (Q2W) in combination with pembrolizumab 400 mg every 6 weeks (Q6W).

The following 3 study arms will be included in the study:

- Arm A: Patients with advanced or metastatic Head and Neck Squamous Cell Carcinoma (HNSCC)
- Arm B: Patients with Melanoma
- Arm C: Patients with Triple-Negative Breast Cancer (TBNC).

Patients will receive intra-tumoral (IT) injections of a fixed concentration of CyPep-1 Q2W beginning at Cycle 1 Visit 1. Pembrolizumab will be administered intravenously (IV) at a fixed dose Q6W beginning at Cycle 1 Visit 1. Patients must be observed for 4 hours post injection for pharmacokinetic (PK) monitoring on Cycle 1 Day 15. The plasma concentration-time profile of CyPep-1 and, if detectable, the derived PK parameters will be assessed.

The dose-limiting toxicity (DLT) period for the Phase 1b portion of the study will be Cycle 1 (initial 6 weeks of study treatment). After the first 6 patients have completed the DLT period, the Data Monitoring Committee (DMC) and Sponsor will review safety and tolerability data prior to the enrollment of the patients into the Phase 2a portion of the study. If ≤2 DLTs are observed in the first 6 patients, then the recommended CyPep-1 dose will be confirmed and enrollment of the remainder of the patients should continue.

If >2 of the 6 patients develop a DLT at the recommended CyPep-1 dose level (5 mg/mL dose concentration), then the maximum tolerated dose (MTD) of CyPep-1 will be assumed to have been exceeded and dose de-escalation will be conducted to determine the MTD. At least 6 patients will be treated at CyPep-1 dose level -1 (2 mg/mL dose concentration). If necessary, due to >2 DLTs in the dose level -1 cohort, a further reduction to dose level -2 (0.5 mg/mL dose concentration) will be performed.

Dose de-escalation will proceed according to the following rules:

- If ≤2 out of 6 patients develop a DLT, the MTD will be declared; or
- If >2 out of 6 patients develop a DLT, the dose will be de-escalated to the next lower dose.

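### No replacement after a first dose, with no visible Phase 1b exception: a non-toxic Cycle 1 exit is counted as no DLT, and the ≤2 threshold then rests on five fully observed patients

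*Protocol*

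**What the plan says.** **Replacement.** Protocol 4.5.3 replaces patients who leave before any dose. For later exits it says: "Patients who are discontinued from the study after receiving at least 1 dose of CyPep-1 or pembrolizumab will not be replaced". The sentence names no phase. The section opens with criteria for Phase 2a patients, but reading the sentence as Phase 2a only would leave the readable Phase 1b text with no replacement rule at all.

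**Dose decision.** Phase 1b is the first 6 patients enrolled, and the DLT window is Cycle 1 (6 weeks). Protocol 3.1.1 sets the timing: "After the first 6 patients have completed the DLT period, the DMC and Sponsor will review safety and tolerability data". The confirmation branch, which SAP 2.3.1 repeats, is: "If ≤2 DLTs are observed in the first 6 patients, then the recommended CyPep-1 dose will be confirmed". The de-escalation branch begins: "If >2 of the 6 patients develop a DLT at the recommended CyPep-1 dose level". No threshold is given for fewer than six.

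**Exits.** Protocol 4.5.2 lists among the reasons for leaving the study: "Patient requests discontinuation or withdraws consent to participate in the study for any reason". Under Protocol 3.1.1.1 a DLT must be judged related to treatment, so a non-toxic exit is not a DLT. Toxic exits are already covered: item 9 counts a treatment-related toxicity that makes the patient stop treatment in Cycle 1, and item 10 counts "Missing >25% of study treatment doses as a result of drug-related AE(s) during the first cycle".

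**Reporting.** Protocol 9.2.2 promises the incidence of DLT events. SAP 3.7.2 lists DLTs on a DLT Evaluable Set. The SAP contents list shows a Section 3.2.3 that is not in the supplied text and may define that set.

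**The concern.** DLT incidence is a Phase 1b primary endpoint and decides whether 20 mg Q2W is confirmed. A patient who withdraws after one injection has had only part of the 6-week window in which to show a DLT. With no replacement and a count over the first 6 enrolled, the unobserved part of that window enters the rule as if it had been free of toxicity. The error runs one way, towards confirming the dose.

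A smaller wording problem sits beside it. The confirmation branch counts DLTs and the de-escalation branch counts patients. One patient with two DLTs plus one patient with one DLT makes three events in two patients, and the two branches then disagree.

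**Working it through.** The documents give no operating characteristics for the DLT rule (the six are described as a practical choice), so there is no stated figure to reproduce. The true DLT rate p and the exit rate e below are assumptions.

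**Inputs from the documents.** Cohort of 6; confirm at ≤2, de-escalate at >2; no replacement after a dose.

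**Step 1: when does the missing patient matter?** With one exit, let d be the number of the other five with a DLT.
- d = 0 or 1: the total is at most 2 whatever the sixth would have shown, so the dose is confirmed.
- d ≥ 3: the total exceeds 2, so the dose is de-escalated.
- d = 2: the total is 2 or 3, so the sixth patient decides.

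With two exits the same reasoning makes 1 or 2 DLTs among the remaining 4 the undecided results.

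**Step 2: size, given one wholly unobserved exit.** Let Xn ~ Binomial(n, p). The full rule confirms with probability P(X6 ≤ 2). Counting the exit as no DLT confirms with probability P(X5 ≤ 2). The two differ only when d = 2 and the sixth would have had a DLT, so the rise is p × P(X5 = 2). At p = 1/3, P(X5 = 2) = 10 × (1/3)² × (2/3)³ = 80/243 = 0.329, and the rise is 0.329/3 = 0.110.

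| p | P(X6 ≤ 2) | P(X5 ≤ 2) | P(X5 = 2) | rise |
|---|---|---|---|---|
| 10% | 0.984 | 0.991 | 0.073 | 0.007 |
| 20% | 0.901 | 0.942 | 0.205 | 0.041 |
| 33% | 0.680 | 0.790 | 0.329 | 0.110 |
| 40% | 0.544 | 0.683 | 0.346 | 0.138 |
| 50% | 0.344 | 0.500 | 0.313 | 0.156 |

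These are upper limits. If the patient is followed for half the window under a constant hazard, the chance of seeing a DLT is q = 1 − (1 − p)^0.5, and P(confirm) = P(X5 ≤ 2)(1 − q) + P(X5 ≤ 1)q. That gives 0.730, 0.605 and 0.408 at 33%, 40% and 50%, so the rise is about 5 to 6 points.

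**Step 3: averaged over exits.** Suppose each of the six leaves independently with probability e before any DLT can be seen. The observed count is then Binomial(6, p(1 − e)). The chance of at least one exit is 1 − 0.95⁶ = 0.265 at e = 5% and 1 − 0.90⁶ = 0.469 at e = 10%.

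| p | P(confirm), e = 5% | rise | P(confirm), e = 10% | rise |
|---|---|---|---|---|
| 10% | 0.986 | 0.002 | 0.988 | 0.004 |
| 20% | 0.913 | 0.012 | 0.924 | 0.023 |
| 33% | 0.713 | 0.033 | 0.744 | 0.064 |
| 40% | 0.586 | 0.041 | 0.627 | 0.083 |
| 50% | 0.392 | 0.048 | 0.442 | 0.098 |

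With half-window observation the per-patient probability becomes p(1 − e) + eq. The rises at 33-50% fall to 0.015-0.020 at e = 5% and 0.029-0.040 at e = 10%.

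**The case against.** A reader might infer that any non-toxic exit leaves the dose rule undefined. The documents do not support that. Completion of the window fixes when the review happens, while the threshold is worded on the first 6 patients. A literal count therefore still returns an answer, and at 2 of 5 that answer is to confirm. What stands is narrower: the literal count silently treats the exit as a non-DLT, which fits poorly with a review timed to completion by all six and with an SAP that names a DLT Evaluable Set.

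Other points against:

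- **The decision is not mechanical.** The DMC and Sponsor review all safety and tolerability data, and Protocol 3.1.3 lets the DMC report a possible change in benefit/risk. An incomplete sixth patient would be visible to them. This stands, and it means the probabilities describe the written rule and not the committee.
- **Exits are partly observed.** Under Protocol 5.5.3.1, "patients must be observed for 4 hours post injection at Cycle 1 Visit 1", and 4.5.3 asks sites to attempt the end-of-treatment assessments. A patient who stops treatment but stays in the study is followed for AEs to 30 days after the last dose. This stands, and it is why the unobserved-exit figures are maxima.
- **DLT rates of 33-50% may be pessimistic.** Protocol Table 5 shows no severe related TEAEs in 14 patients (3 + 5 + 6) of the earlier CICILIA study. That is only indicative for the combination, but at 10-20% the averaged effect is small.
- **Handling may exist elsewhere.** SAP 3.2.3, Protocol 5.1-5.2 and the DMC charter are not in the supplied text. The lack of a visible definition of the DLT Evaluable Set is therefore not a fault in the plan.
- **Denominators are promised.** SAP 3.1.5 says percentage denominators will be defined, and SAP 3.3.3 tabulates the analysis populations. Little remains of a reporting complaint beyond the fact that readable SAP 3.7.2 provides a listing and no n/N.

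**Conclusion.** The point holds as a minor, cheap improvement. As written, the no-replacement sentence lets the ≤2 threshold be met with five fully observed patients, and it resolves the missing observation in favour of confirmation. One exit matters only at exactly 2 of 5, and two exits at 1-2 of 4.

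The largest effect, 11-16 points, needs an exit that is wholly unobserved and a true DLT rate of 33-50%. Averaging over exit rates of 5-10% brings it to at most 3-10 points, and DLT rates of 10-20% bring it to about 0.2-2 points. All of these rest on assumed DLT and exit rates, independent patients and no use of judgement by the DMC or Sponsor.

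It would be wrong to infer that this trial's dose confirmation was compromised: the documents do not show that any of the six left early. SAP Section 1 states that the study ended after Phase 1b, so the remaining effect is on how the confirmation is reported and on any reuse of the design.

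**What to change.** **Protocol 4.5.3.** Add a Phase 1b exception: a patient who is not DLT-evaluable for a reason other than a DLT, whether through study exit or too little Cycle 1 exposure, is replaced from the planned 90 until six are evaluable. Covering low exposure as well as exit matters, because a patient who stays in the study with one injection would otherwise again leave five.

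**Definition.** A patient is DLT-evaluable if a DLT occurs in Cycle 1 (assessed first), or if the 6-week window is completed with a stated minimum exposure. Pembrolizumab plus at least 2 of the 3 CyPep-1 injections is one option. It is a suggestion and does not follow from DLT item 10, which states no denominator: one missed injection is 1/3 of CyPep-1 doses or 1/4 of all Cycle 1 doses.

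**Early review.** With d patients with a DLT and m patients missing, proceed without waiting if d + m ≤ 2 or d ≥ 3. This covers one exit and two.

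**Wording.** State both branches as patients with at least 1 DLT.

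**SAP.** Check that the DLT Evaluable Set agrees with this definition, and report DLT incidence as n/N beside the listing. With the study ended, this is the part that can still be done.

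**Cost.** One exception, one definition, one early-review sentence and one table row; total N is unchanged. Each replacement can delay the review by up to about 10 weeks (28 days of screening plus 6 weeks of observation), but only when the missing patient could change the decision. For a single exit that is the 2-of-5 case: about 31-35% of such exits at DLT rates of 33-50%, and fewer at lower rates.

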5.3 Randomization and Blinding

This is an open-label, non-randomized study. No blinding is necessary.

5.4 Breaking the Blind

Procedures for breaking the blind are not applicable for this study.

5.5 Drug Supplies

5.5.1 Formulation and Packaging

The IT formulation of CyPep-1 is a clear and colorless aqueous solution (5 mg/mL) for subcutaneous administration supplied in single-use vials. The CyPep-1 (5 mg/mL) solution consists of the drug substance CyPep-1 dissolved in 0.9% sodium chloride solution. Each vial contains a deliverable volume of 2 mL of CyPep-1 solution that contains 10 mg of CyPep-1 and corresponding to 14 mg of acetate salt. An additional overfill is included in each vial to ensure that the labelled amount of 10 mg of CyPep-1 (corresponding to 14 mg of the acetate salt) can be delivered.

Pembrolizumab is formulated as a 100 mg/4 mL (25 mg/mL) clear to slightly opalescent, colorless to slightly yellow solution in single-dose vials.

CyPep-1 and pembrolizumab will be supplied by Cytovation ASA.

CyPep-1 and pembrolizumab will be labelled in compliance with the legal requirements of each country. The label text will also be translated and/or adjusted, to follow applicable regulatory requirements (eg, Clinical Trials Regulation EU No 536/2014 [Annex 6]), national laws in force, and in accordance with the local languages. In addition, each label will include storage conditions for the drug without the information about the study.

5.5.2 Study Drug Preparation and Handling

The study drugs must be received by a designated person at the study site, handled safely and properly, and kept in a secured location to which only the Investigator, Pharmacist, and designated assistants have access. Upon receipt of the study drugs, all supplies should be stored according to the instructions specified on the study drug labels. See Section 5.5.5 for details of storage condition.

The Pharmacy Manual contains specific instructions for the preparation of CyPep-1 and pembrolizumab administration solutions.

5.5.3 Study Drug Administration

The overall study treatment regimen is defined as IT CyPep-1 in combination with IV pembrolizumab.

5.5.3.1 CyPep-1 administration

The study Investigator will identify qualified staff who will perform IT injections and this decision will therefore be made on a site-by-site basis. The Sponsor will provide training on lesion selection and IT injection to Investigators participating in the study as part of the protocol training.

Lesions appropriate for IT injection will be determined following assessment of procedural and operational complexity and risk. While deeper lesions may be targeted, cutaneous lesions that are injectable without imaging will be prioritized. Further details regarding selection of tumor lesions as well as recommendations for IT injection procedures will be provided to Investigators and staff in the Guidance for Intra-tumoral Administration of CyPep-1 study manual.

Premedication with an antihistamine IV or oral equivalent should be administered approximately 30 to 60 minutes prior to the first IT dose of CyPep-1. Premedication should be administered prior

to subsequent CyPep-1 doses based upon clinical judgment and presence/severity of prior reactions. This regimen may be modified based on local treatment standards and guidelines as appropriate. Patients should be well hydrated prior to CyPep-1 administration.

CyPep-1 will be administered Q2W as an IT injection. CyPep-1 will be administered through a needle, which should be redirected along multiple tracks to ensure even dispersion of CyPep-1 throughout the tumor lesion. On the visits that CyPep-1 and pembrolizumab are administered on the same day, CyPep-1 is to be administered 30 to 60 minutes **after** pembrolizumab infusion is completed. Following CyPep-1 administration, patients must be observed for 4 hours post injection at Cycle 1 Visit 1 and Cycle 2 Visit 1 and 1 hour post injection at Cycle 1 Visit 2 and Cycle 1 Visit 3 for potential immediate injection-related reactions. Refer to the Guidance for Intra-tumoral Administration of CyPep-1 study manual for more details.

